6.2.4 Emergency measures

See Sections Warnings and Overdosage in the Prescribing Information.

6.3 Concomitant therapy

All concomitant medications and therapies (prescribed and non-prescribed) must be recorded in the case report form, with trade name (generic name), route or formulation, dosing scheme, the indication and start and stop dates of administration. Any change during the study should be documented as well.

6.3.1 Permitted therapy

6.3.1.1 Antiemetics

Vomiting was not a dose-limiting toxicity in the phase I clinical trial with AESZ-108. In phase II clinical trials completed in endometrial (n = 43) and ovarian (n = 42) cancer patients, no vomiting of grade 3 or 4 was observed following AEZS-108 at a dose of 267 mg/m².

According to the current ASCO guideline for “Antiemetics in Oncology” (2011) [3], AEZS-108 should be considered a chemotherapeutic agent with “low emetic risk” and therefore, before start of AEZS-108 infusion, prophylactic antiemetic treatment with 8 mg dexamethasone is recommended.

If additional symptomatic antiemetic treatment is needed, this should be started with an antiemetic with predominantly local/peripheral mode of action, like metoclopramide (Paspertin®), alizapride (Vergentan®).

If local/peripheral type antiemetics prove to be ineffective in a given patient, antiemetics with a predominantly central mode of action (5-HT₃-antagonist, e.g. ondansetron (Zofran®)) will be used.

Antiemetics that were started as symptomatic treatment should also be given as prophylactic treatment in subsequent treatment cycles of the same patient.

6.3.1.2 Anti-allergic treatment

In case of an allergic reaction, treatment should consist of a step-by-step approach of general measures, such as adequate shock positioning, volume substitution, and the administration of appropriate drugs like epinephrine (0.1 to 1.0 mg), H₁- and H₂-receptor antagonists (dimetidene 4.0 to 8.0 mg, cimetidine 200 to 400 mg), and corticosteroids (prednisolone 0.5 to 1.0 g).

In patients that have experienced an allergic reaction during treatment with AEZS-108, prophylactic anti-allergic medication (like combined application of dimetidene and cimetidine) should be administered in subsequent treatment cycles.

6.3.1.3 Other

The following are permitted:

- In case of a delayed hematological recovery, hematopoietic blood components may be administered as needed.
- Colony stimulating factors should not be administered prophylactically during the first cycle of AEZS-108 or doxorubicin. From cycle 2 onwards, prophylactic use is at the discretion of the treating physician.
Therapeutic use of colony stimulating factors in patients with hematotoxicity is permitted in any cycle.
- Supportive and palliative treatment without an anticancer effect (nutritional, transfusional support, pain control, bisphosphonates for bone metastases, etc.).

6.3.2 Prohibited therapy

Concomitant medication and treatments that may not be administered are:

- concomitant anticancer therapies (including treatment with another investigational drug and chemo-, immune-, hormone-, or radiotherapy, but excluding irradiation of non-indicator lesions for symptom relief),
- live vaccines
- amiodarone
- sotalol.

6.3.3 Interaction with other medicinal products and other forms of interaction

AEZS-108 may interact with other medicinal products in the same manner as doxorubicin. Therefore, based on doxorubicin's Prescribing Information, the following is a list of drugs

(other than those listed in section 6.3.2) potentially requiring precautions also when used with AEZS-108:

- Amphotericin B
- Antiepileptic drugs such as carbamazepine, phenytoin, valproate
- Cardioactive drugs, such as calcium channel blockers(e.g. verapamil)
- Cyclosporin
- Cimetidine
- Clozapine
- Digoxin
- Heparin
- Hepatotoxic drugs
- Inducers of CYP450, such as rifampicin and barbiturates
- Inhibitors of CYP450, such as fluvoxamine, ciprofloxacin, gemfibrozil, fluconazole, bupropion, cinacalcet, fluoxetine, paroxetine, quinidine, indinavir, nelfinavir, ritonavir, clarithromycin, itraconazole, ketoconazole, nefazodone, saquinavir, suboxone and telithromycin
- Progesterone
- Radiation therapy (preceding, concomitant or subsequent)
- Ritonavir
- Substances influencing the bone-marrow function such as amidopyrine derivatives, antiretroviral drugs, chloramphenicol, phenytoin, sulphonamides
- Uric acid lowering agents

Examples of precautions are monitoring of cardiac function, monitoring of hemato/hepato/nephrotoxicity and dose adjustment. The investigator is referred to doxorubicin's Prescribing Information to identify which precaution(s) must be applied specifically to each drug listed above also when used concomitantly with AEZS-108.

6.4 Follow-up treatment (no crossover after the end of study treatment)

For a patient who requires further treatment for her malignant disease, after the end of study treatment with AEZS-108 or doxorubicin, the selection and timing of such treatment is at the discretion of the investigator. As there is no standard of care treatment in these cases, he/she will take into account the current signs and symptoms of the disease and, where applicable, any persisting drug-related adverse events (i.e., causality at least possibly related).

A patient who fails on either study treatment will NOT be allowed to cross over to the alternative study treatment.

7 ASSESSMENTS

The following endpoints will be assessed:

1. Overall survival (primary efficacy endpoint).
- 2a Efficacy: progression-free survival (PFS), overall response rate (ORR = CR + PR), and a clinical benefit rate (CBR) will be evaluated as CR + PR + SD for at least 3 months.
- 2b. Safety: adverse events, clinical laboratory, ECG and LVEF.
- 2c. Quality of Life: EORTC QLQ30 + QLQ-EN24 questionnaires.

Pharmacokinetic and electrocardiographic parameters of the PK sub-study are described in [APPENDIX 7](#) of the protocol.

Evaluation of exposure-response relationship and population pharmacokinetic evaluations will be described in the Statistical Analysis Plan.

7.1 Efficacy (RECIST)

Response and progression will be evaluated using the international criteria proposed by the revised Response Evaluation Criteria in Solid Tumors (RECIST) guideline (version 1.1) [6]. Changes in the largest diameter (unidimensional measurement) of the tumor lesions and the shortest diameter in the case of malignant lymph nodes are used in the RECIST criteria.

During ongoing treatment, patients should be re-evaluated for response every 3 cycles (i.e. every 9 weeks).

The following text is a summary of RECIST 1.1.

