6.1.3 Treatment modifications / delay of treatment

Any deviation from the planned dosing schedule must be commented on in the CRFs.

Delay of re-treatment: Subsequent cycles of study treatment should not begin before a patient has recovered to CTCAE Grade 1 from a drug-related adverse event (i.e., causality at least possibly related) that the investigator feels is clinically significant. No treatment delay is required for alopecia or anemia for which supportive therapy should be given according to study sites' clinical practice (see also 6.3.1.3). Re-treatment may be postponed for up to 2 weeks. A patient who has not recovered within 5 weeks after the last dose should be withdrawn and followed up as required.

Dose reduction: Any of the following drug-related adverse events (i.e., causality at least possibly related) will require a dose modification, if its duration exceeds the indicated period:

- Grade 4 neutropenia [ANC < 500/mm³] lasting 7 days or more

- Grade 3 febrile neutropenia lasting for more than 7 days
[Grade 3 defined as: ANC < 1000/mm³ with a single temperature of >38.3 °C (101 °F) or a sustained temperature of ≥ 38 °C (100.4 °F) for more than one hour]
- Grade 4 febrile neutropenia (of any duration)
[Grade 4 defined as: Life-threatening consequences; urgent intervention indicated]
- Grade 3 thrombocytopenia [Platelet count: < 50,000 – 25,000/mm³] persistent at the scheduled time of re-dosing (i.e. blood sample on the day before re-dosing) and associated with a clinical risk of bleeding (presenting, e.g. as hemorrhagic diathesis: petechial rash, especially affecting tunica mucosa in oral cavity, gingival rash or petechial skin rash associated with prolonged bleeding time, e.g. in the Duke bleeding time test)
- Any other Grade 4 hematological toxicity (except for lymphocytopenia) lasting 7 days or more
- Grade 3 nausea/vomiting/diarrhea lasting 5 days or more despite optimal medical management.

If any of the above dose-limiting toxicities occurs and re-treatment is indicated after the toxicity has resolved to ≤ Grade 1 within the allowed period for a treatment delay, then dosing will be resumed with a dose reduction.

Dose Level	AEZS-108 Dose (mg/m ²)
Starting Dose	267
1 st Dose Reduction (approximate 20 % reduction)	210
2 nd Dose Reduction (approximate 40 % reduction)	160

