7.1.1 Confirmatory Measurement

A subsequent scan must be obtained no earlier than 4 weeks following the initial documentation of an objective status of either complete response (CR) or partial response (PR).

Note: During ongoing treatment, the next scheduled follow-up measurement would be due after three more cycles, i.e., 9 weeks later in absence of treatment delays). In order not to miss the confirmation of the response, or if a patient will go off treatment, a separate imaging session should be scheduled, however, no earlier than 4 weeks after the previous imaging.

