8.4 Procedures during treatment

8.4.1 Procedures on Cycle 1 Day 1 (date of first study treatment)

After randomization, but prior to first administration of study treatment, each patient will have the following assessments and tests:

- **Interval history** and symptom-directed examination
Findings to be recorded as Medical History / Concomitant Disease/Condition
- **Clinical assessments** (including ECOG performance status, blood pressure, pulse, and weight for BSA and dose calculation)
- **Clinical laboratory** tests (hematology, chemistries, urinalysis)
- **Eligibility criteria review**
In the absence of new findings that would violate any of the eligibility criteria,

except for Day 1 clinical laboratory tests, the patient may receive the allocated study treatment.

- **Study treatment**
Administration of allocated study medication at the recommended starting dose.
- **Sparse PK sampling (AEZS-108 treated patients only)**
Blood collections within the following time windows:
sample #1: within 60 minutes before end of the 2-hour infusion
sample #2: between 30 and 60 minutes after the end of infusion (EOI)
sample #3: between 120 and 180 minutes after EOI;
sample #4 (optional): between 4 and 6 hours after EOI.

A patient, in whom sparse PK sampling was not possible in Cycle 1, may have the samples taken at any subsequent cycle. It is not planned to have repetitive sparse sampling of the same patient during multiple cycles.
- **PK substudy (instead of ‘sparse PK sampling’, at selected investigational sites only)**
Procedures related to the PK substudy are described in Appendix 7 of the protocol.

8.4.2 Weekly procedures during Cycle 1

Once weekly controls during Cycle 1 will include the following:

- **Clinical assessments** (including blood pressure and pulse)
- **Clinical laboratory tests** (hematology, chemistries, urinalysis)
- **Adverse event** recording.

Retreatment is planned in 3-weekly intervals, i.e. Day 1 of new cycle is corresponding to Day 22 of the previous cycle. In case of incomplete recovery from hematological toxicity or adverse events, re-treatment may be delayed for up to 2 weeks, i.e. with appropriate supplementary weekly controls on Day 29 and Day 35 (see [Section 6.1.3](#)).

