8.4.4 Procedures during Cycle 2-9

Depending on hematological toxicities and any safety issues observed during Cycle 1, scheduling of hematological controls and/or other investigations is at the discretion of the investigators. For tests performed by a laboratory not affiliated with the study site (e.g. mid-cycle controls by the patient's home doctor) copies of the external laboratory reports will be provided to the sponsor and results reported in the CRF.

Adverse findings in such controls/investigations/diaries that the investigator considers as clinically important/significant will be recorded as Adverse Event.

8.4.5 Procedures at the end of Cycle 3 and 6

The following assessments will be performed at end of Cycle 3 and Cycle 6, i.e. together with the assessments required to assure continuation of study treatment with Cycle 4 and Cycle 7, respectively.

- **Cardiac function:**
 - Left ventricular ejection fraction (LVEF): echocardiogram or MUGA

Note: Recommended to be conducted also at end of Cycle 7 and 8 (i.e., before start of Cycle 8 and Cycle 9, respectively) for both arms. Results are to be captured on the eCRF if there is an abnormal finding.
- **Quality of Life:** questionnaires
- **Tumor imaging (CT or MRI):** evaluation of time-point response by comparison with target and non-target lesions defined at screening (baseline)

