### **4.3 Tumor Assessment Schedule**

Tumor assessments will occur every 3 cycles ( $\pm 7$  days) during ongoing treatment, then if required beyond the end of treatment every 3 months ( $\pm 7$  days) while the patient is on study. The last assessment will occur when approximately 384 randomized patients have died.

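### On-treatment scans follow dosing cycles rather than calendar weeks, so unequal dose delays could bias PFS and shift CBR, by an amount and in a direction the documents do not settle

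*Protocol*

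**What the plan says.** Protocol 7.1 treats three cycles and nine weeks as the same interval: "During ongoing treatment, patients should be re-evaluated for response every 3 cycles (i.e. every 9 weeks". Protocol 7.1.1 qualifies this: the next scheduled measurement is due "i.e., 9 weeks later in absence of treatment delays".

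The operative schedule is in cycles. Protocol 8.4.5 states "The following assessments will be performed at end of Cycle 3 and Cycle 6", and places them "together with the assessments required to assure continuation of study treatment with Cycle 4 and Cycle 7, respectively". SAP 4.3 says "Tumor assessments will occur every 3 cycles", with a ±7-day window and no calendar anchor; SAP 7.2.1 and Protocol 9.5.2 repeat this.

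On cycle length, Protocol 8.4.2 says "Retreatment is planned in 3-weekly intervals", and Protocol 6.1.3 adds "Re-treatment may be postponed for up to 2 weeks". Protocol 6.2.3 applies the same rule to doxorubicin. In both arms a patient not recovered within 5 weeks of the last dose is withdrawn from treatment.

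SAP 7.2.5 compares PFS by an ordinary log-rank test. The PFS sensitivity analyses in SAP 7.2.6 vary the population, the covariates and a best-response subset; none deals with assessment timing. The one rule for late assessments, in SAP Appendix B (12.2.3), is marked as not relevant to this trial.

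**The concern.** A dose delay moves the scan that follows it. Because the window is set around the end of the cycle, a scan taken weeks after week 9 still counts as on schedule. Progression is usually dated when it is seen, so the arm with more delays has its progressions recorded later even if the disease behaves identically in both arms.

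SAP 7.4 tests PFS second, after OS, for a possible labelling claim. The trial is open label and delays are driven by toxicity, so scan timing can depend on treatment. CBR is exposed as well, because it rests on disease status at a minimum time and is read at scans whose timing also moves.

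**Working it through.** **The plan's own figure.** 3 cycles × 3 weeks = 9 weeks. Reproduced, for patients with no delay.

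**Range with permitted delays.** The longest dose-to-dose interval is 3 + 2 = 5 weeks.
- First scan: 3 × 3 = 9 weeks to 3 × 5 = 15 weeks.
- Second scan: 6 × 3 = 18 weeks to 6 × 5 = 30 weeks.
- If only doses 2 and 3 are late and the scan is on Day 21 of Cycle 3: 5 + 5 + 3 = 13 weeks.

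Weeks 15 and 30 need the full delay in every cycle.

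**Delay rates in the documents.** Protocol 1.2.2 reports that fewer than 10% of earlier AEZS-108 patients were delayed for hematotoxicity, by one to two weeks. No doxorubicin rate is given, so the rates below are assumptions.

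**Effect on PFS.** Null simulation: 250 patients per arm, the same exponential PFS in both, progression seen at scans after cycles 3, 6 and 9 and then every 12 weeks, two-sided log-rank test at 0.05. The documents give no planning value for median PFS, so 13, 20 and 30 weeks were used (the Phase II median TTP was about 7 months). HR is the less-delayed arm over the more-delayed arm.

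| Assumed delays | Median (weeks) | Spurious HR | False-positive rate |
|---|---|---|---|
| None | 13 | 1.00 | 4–6% |
| 10% vs 50% of patients, 1 week per 3 cycles | 13 | 1.08 | 14% (repeat runs about 8–14%) |
| Same, 2 weeks | 13 | 1.05 | 9% |
| Same, 6 weeks | 13 | 1.07 | 12% |
| 10% vs 30% of patients | 13 | 1.01–1.04 | 5–8% |
| 10% vs 50% of patients | 20 | 1.00–1.05 | 5–9% |
| 10% vs 50% of patients | 30 | 0.97–1.03 | 4–7% |
| 10% vs 50%, 30% of events dated exactly | 13 | – | 5–7% |
| 2 weeks in 5% vs 15% of cycles | 13–30 | 1.04–1.07 | 8–13% |
| 2 weeks in 5% vs 30% of cycles | 13–30 | 1.05–1.10 | 10–16% |
| Every patient: 9 vs 15 weeks | 13–30 | 1.09–1.18 | 16–43% |

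Scenarios used 400 to 2,000 runs. At 400 runs, a rate of 10% has a standard error of √(0.10 × 0.90 / 400) = 1.5 points. The rate does not rise steadily with the length of delay, because the log-rank test uses only the order of the detection dates. Equal delays in both arms (5% of cycles each) gave HR about 1 and 4–5%.

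**Which arm gains.** At 10% vs 50% and a 13-week median, the less-delayed arm falsely wins in about 0.3–1.2% of runs, against a nominal 2.5%. Nearly all the excess goes to the more-delayed arm.

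**Effect on CBR.** With an exponential 20-week median, the proportion progression-free at week t is 2^(−t/20). A patient qualifies if progression-free at a scan at or after the threshold; 3 months is taken as 13 weeks.

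| First and second scan | 9-week definition | 3-month definition |
|---|---|---|
| Weeks 9, 18 (no delay) | 2^(−9/20) = 73% | 2^(−18/20) = 54% |
| Weeks 12, 24 | 2^(−12/20) = 66% | 2^(−24/20) = 44% |
| Weeks 15, 30 (ceiling) | 2^(−15/20) = 59% | 2^(−15/20) = 59% |

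Under the 9-week definition (Protocol 9.5.2, SAP 7.2.1) delay lowers CBR. Under the 3-month definition (Protocol synopsis and section 7) it lowers CBR until the first scan passes week 13, and can then raise it.

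**The case against.** The delay rule is identical in both arms, so there is no bias without a difference in delay rates, and the documents show none. That stands.

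A reader might infer that the drugs differ in myelotoxicity and that the plan therefore favours the more toxic one. The documents do not support that. Protocol 1.2.1 describes the hematological toxicity of the two drugs in animals as qualitatively similar, and no clinical comparison is given.

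A reader might also infer a false PFS claim for AEZS-108. That would need AEZS-108 to be the more-delayed arm, which nothing indicates. Its one reported rate is low, although it covers hematotoxicity only. If doxorubicin were delayed more, the bias would work against AEZS-108. PFS is also tested only if OS succeeds.

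The simulation overstates the effect in one respect. It has no unscheduled scans, whereas Protocol section 4 allows earlier reassessment on suspected progression, and SAP 7.2.4 dates progression found between visits when documented and dates deaths exactly. It also omits the SAP 7.2.4 rule that censors PFS when treatment stops for toxicity, which would remove some of the most-delayed patients. Both points stand. They limit the size but do not remove the mechanism, because nothing in the plan would detect or correct a timing difference.

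**Conclusion.** The point holds as a conditional weakness in a key secondary endpoint. Scan timing depends on dosing, the permitted range for the first scan is 9 to 15 weeks with 15 a ceiling rather than a typical value, and the SAP has no correction.

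With 10% versus 50% of patients delayed, the spurious PFS hazard ratio is about 1.02–1.08 and the false-positive rate about 5–14%. The top of that range needs a 13-week median and no unscheduled scans. Under the same delay rates it is near nominal at a 30-week median or when many progressions are dated by unscheduled scans. Larger figures come only from the heavier per-cycle delays or the all-patients extreme, which are assumptions too.

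A reader might infer that CBR is inflated in the more-delayed arm. Under the SAP's 9-week definition it falls; under the 3-month definition it can go either way. The primary OS analysis and its 384-death design are unaffected.

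**What to change.** In Protocol 7.1, 7.1.1, 8.4.5, 9.5.2 and the flow chart, and in SAP 4.3 and 7.2.1, schedule on-treatment imaging at weeks 9, 18 and 27 from randomisation (±7 days) in both arms, regardless of dose delays. Apply the missed-visit censoring rule in SAP 7.2.4 to those dates. Use one CBR definition throughout, with a stated scan window. With calendar scans the simulated null rejection rate returns to about 4–6%.

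The cost is a short amendment. Some scans will not coincide with a dosing visit. In an undelayed nine-cycle patient the ninth dose is at 8 × 3 = 24 weeks and the end-of-therapy scan 3 to 5 weeks later, at weeks 27 to 29, so the week-27 scan roughly coincides with it. A patient with delayed cycles may have one extra scan before end of therapy. The change to 12-weekly scans when treatment stops remains and still depends on treatment.

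The current SAP is dated March 2017, after the study end planned in the synopsis (December 2015), so imaging may no longer be changeable. In that case add to SAP 7.2.6 a PFS sensitivity analysis that is either interval-censored or dates progression at the scheduled assessment, and tabulate actual scan times by arm. This costs only programming. Neither route implies any change to the dose-delay rules.

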7.1.1 Confirmatory Measurement

A subsequent scan must be obtained no earlier than 4 weeks following the initial documentation of an objective status of either complete response (CR) or partial response (PR).

Note: During ongoing treatment, the next scheduled follow-up measurement would be due after three more cycles, i.e., 9 weeks later in absence of treatment delays). In order not to miss the confirmation of the response, or if a patient will go off treatment, a separate imaging session should be scheduled, however, no earlier than 4 weeks after the previous imaging.

7.1.2 Definitions

Evaluable for toxicity. All patients will be evaluable for toxicity from the time of their first treatment with the study drug.

Evaluable for objective response. Only those patients who have measurable disease present at baseline, have received at least one cycle of therapy, and have had their disease re-evaluated will be considered evaluable for response. These patients will have their response classified according to the definitions stated below. (Note: Patients who exhibit objective disease progression prior to the end of cycle 1 will also be considered evaluable.)

Evaluable Non-Target Disease Response. Patients who have lesions present at baseline that are evaluable but do not meet the definitions of measurable disease, have received at least one cycle of therapy, and have had their disease re-evaluated will be considered evaluable for non-target disease. The response assessment is based on the presence, absence, or unequivocal progression of the lesions.

7.1.3 Disease Parameters

Measurable disease. Measurable lesions are defined as those that can be accurately measured in at least one dimension (longest diameter to be recorded) as ≥ 20 mm by chest x-ray, as >10 mm with CT scan, or ≥ 10 mm with calipers by clinical exam. All tumor measurements must be recorded in millimeters (or decimal fractions of centimeters).

Note: Tumor lesions that are situated in a previously irradiated area will be considered measurable (and eligible as target lesion) if they have developed or progressed after the irradiation.

Malignant lymph nodes. To be considered pathologically enlarged and measurable, a lymph node must be >15 mm in short axis when assessed by CT scan (CT scan slice thickness recommended to be no greater than 5 mm). At baseline and in follow-up, only the short axis will be measured and followed.

Non-measurable disease. All other lesions (or sites of disease), including small lesions (longest diameter <10 mm or pathological lymph nodes with ≥ 10 to <15 mm short axis), are considered non-measurable disease. Bone lesions, leptomeningeal disease (*not applicable in this study*), ascites, pleural/pericardial effusions, lymphangitis cutis/pulmonitis, inflammatory breast disease, and abdominal masses (not followed by CT or MRI), are considered as non-measurable.

Note: Cystic lesions that meet the criteria for radiographically defined simple cysts should not be considered as malignant lesions (neither measurable nor non-measurable) since they are, by definition, simple cysts.

‘Cystic lesions’ thought to represent cystic metastases can be considered as measurable lesions, if they meet the definition of measurability described above. However, if non-cystic lesions are present in the same patient, these are preferred for selection as target lesions.

Target lesions. All measurable lesions up to a maximum of 2 lesions per organ and 5 lesions in total, representative of all involved organs, should be identified as target lesions and recorded and measured at baseline. Target lesions should be selected based on their size (lesions with the longest diameter), be representative of all involved organs, but in addition should be those that lend themselves to reproducible repeated measurements. It may be the case that, on occasion, the largest lesion does not lend itself to reproducible measurement in which circumstance the next largest lesion that can be measured reproducibly should be selected. A sum of the diameters (longest for non-nodal lesions, short axis for nodal lesions) for all target lesions will be calculated and reported as the baseline sum diameters. If lymph nodes are to be included in the sum, then only the short axis is added into the sum. The baseline sum diameters will be used as reference to further characterize any objective tumor regression in the measurable dimension of the disease.

Non-target lesions. All other lesions (or sites of disease) including any measurable lesions over and above the 5 target lesions should be identified as non-target lesions and should also be recorded at baseline. Measurements of these lesions are not required, but the presence, absence, or in rare cases unequivocal progression of each should be noted throughout follow-up.

